
Statistical Considerations:
	
The full details of the analysis will be provided in the statistical analysis plan, which will be finalised prior to database lock.
 
The primary outcome (number of respiratory infections between 6 and 9 months of age) will be compared between the two groups of 1st MMR timing (Group M.C. and M.M. vs. Group C.M. and C.C.) using negative binomial regressions, adjusted for sex (male/female), day-care attendance (yes/no), presence of comorbidities (yes/no), older siblings (yes/no), and will be presented as adjusted incidence rate ratios (aIRRs) with 95% confidence intervals.
 
Other comparative analyses at the 9-months and 2-years endpoints will be done using chi-square test (or Fisher's test when appropriate) for categorical variables, and paired t-test or Wilcoxon signed-rank test for continuous variables, depending on the distribution of the variable. Time-to-event outcomes will be assessed using Cox proportional hazards with adjustment for baseline risk factors.
 
For the 2-years endpoints, factorial analysis will enable to measure the effect on all outcomes of the intervention made to the first and the second dose of MMR, separately or in combination.
 
Regression will be used to identify independent factors associated with each of the outcomes. All significant predictors (<math>p < 0.20</math>) will be then included in a stepwise backward multivariate analysis.
 
Trauma and accident outcomes will also be compared between the two groups and will act as control events, as MMR is not believed to change their risk of occurrence.
 
Subgroup analysis are planned (by sex, risk factor, underlying maternal immunity, etc.).
 
The analyses will be done in collaboration with the Clinical Research Center at Geneva University Hospitals.

GCP Statement:
	
This study will be conducted in compliance with the protocol, the current version of the Declaration of Helsinki, ICH-GCP, as well as all national legal and regulatory requirements.

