### 6.2 Methods of minimising bias

#### 6.2.1 Randomisation

Consent to blood tests at 6, 9 and 24 months of age will be sought, and will determine whether a child participates in Part 1 only, or both Part 1 and Part 2. Participant will be randomly allocated at inclusion to four equal groups, using a web-based randomisation procedure, stratified by consent to blood tests (yes/no), in randomly permuted blocks of variable length (4 or 8), enabling to prevent predictability of intervention assignments. The randomisation lists will be generated prior to the initiation of the study by someone not involved in the study analysis and will be integrated into REDCap.

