## 7. STUDY POPULATION

### 7.1 Eligibility criteria

#### 7.1.1 Inclusion criteria

Participants fulfilling all of the following [inclusion](#) criteria are eligible for the study:

- 1) Informed Consent as documented by signature
- 2) 6-month-old children
- 3) In overall good health, without any clinically significant concomitant disease states (e.g., renal failure, hepatic dysfunction, cardiovascular disease, etc.) and no clinically significant abnormal finding on history and/or physical examination
- 4) Fully immunised for age according to the Swiss vaccination schedule
  - a) with at least 2 doses of DTP-containing vaccine
  - b) the last dose of vaccine received at least 2 weeks prior to enrolment

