### 9.2 Assessments of outcomes

#### Clinical outcomes

##### Source of information:

- 1) Online parent questionnaires sent every two weeks for the first 3 months, then monthly.
- 2) Contact with the treating paediatrician at 9 and 24 months for completion of any missing illness data.
- 3) Access to medical records.

The data collected (Table 4) will enable the extraction of the following measurement for each participant for both infectious and allergic episodes: number of episodes between 6 months and 2 years of life, interval between inclusion and first episode, characteristics of each episode (e.g. diagnosis, duration) and treatment (e.g. type, route, duration), complications, hospitalisation (e.g. reason, length of stay, outcomes), number of days free of episode. Episodes of trauma/accidents will be used as control events.

Data collected at inclusion, confirmed with treating paediatrician and hospital records
Demographics: parental age, education, ethnicity, country of birth; household composition, age of siblings; location of home (countryside, urban); socioeconomic group; date of birth*.
Potential confounding and or mediating factors pre-randomisation: maternal pregnancy factors (mode of delivery, infection, antibiotics, probiotics, smoking, supplements, vaccines), infant factors (sex, gestational age, season of birth, sepsis, antibiotics, probiotics, alimentation, supplements and medications); family history of allergic disease (eczema, hay fever, asthma, food and non-food allergies); household smoking; pet exposure.
Data collected with online questionnaires, confirmed with treating paediatrician and hospital records
Infection outcome data: episodes of: upper/lower respiratory tract infection (including croup, pharyngitis, otitis media, bronchiolitis, bronchitis, pneumonia), cold sores/mouth ulcers, gastroenteritis, urinary tract infection, bone-joint infection, other infection.  For all infections: diagnosis, pathogen(s), site of infection, date, symptoms, duration, severity, outcome, health care use, hospital admission (more than 1 day), treatment.
Trauma/accident data (used as control events): medically attended accidents, burns or trauma.  For all occurrences: date, severity, health care use, hospital admission (more than 1 day).

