Allergic disease outcome data: presence of eczema, food allergy, wheezing disease.  Eczema - diagnosis using adapted version of the UK diagnostic tool,  parent-reported doctor-diagnosed, and clinical evaluation during study visits; symptoms; severity and impact on quality of life using the POEM  and the SCORAD  scores.  Food-allergy – parent-reported doctor-diagnosed food allergy or sensitisation; diagnostic test used: participants with suspicion of food allergy will be seen by a specialist, as routinely done in Geneva. As recommended,  diagnosis will be made using oral food challenge, basophil activation test, or mast cell activation test; sensitisation defined using skin prick tests results and serum-specific IgE concentration (including allergen component-resolved diagnostics).  Wheezing diseases – parent-reported doctor-diagnosed wheezing episode (bronchiolitis or infant asthma).   For each allergic disease: age at diagnosis, date, duration and severity of episodes/flare, outcome, treatment.
Potential confounding factors post randomisation: breastfeeding (age at cessation); formula (type); solid feeding (age at introduction of different foods); smoking exposure; childcare attendance (index & siblings); travel; pet exposure; vitamin D supplementation; probiotic intake; paracetamol/ibuprofen use; antibiotics; other vaccinations (which and when).

Table 4: Summary of clinical data that will be collected.

\* Collection of participants' date of birth is needed to determine the season of birth (see table 4 above), as well as the time range for the visits (see section 9.3).

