#### 11.4.2 Primary Analysis

This will be a classic 2-arm trial with regard to the first intervention (early 1st dose of MMR) and the primary outcome (number of respiratory infections between 6 and 9 months of age). The analysis of the

primary outcome will be performed by means of a regression model (either logistic, if the primary outcome is dichotomised as 0 vs  $\geq 1$ , or negative binomial, if numbers of infection episodes are left uncategorized) and will compare the two group of 1st MMR timing (Group M.C. or M.M. vs. Group C.M. or C.C.). The model will be adjusted for sex (male/female), day-care attendance (yes/no), presence of comorbidities (yes/no), older siblings (yes/no), and will be presented as adjusted odd ratios, hazard ratio, or incidence rate ratios (aIRRs) with 95% confidence interval, according to the model chosen.

It will be done in collaboration with the Clinical Research Center at Geneva University Hospitals, once all participants have attended the 9 months visit.

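### The primary model's covariate list omits the randomisation stratum and season, and gives day-care attendance no time point although Table 4 lists it only after randomisation

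*Protocol*

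**What the plan says.** **Covariates.** Protocol section 11.4.2 states: "The model will be adjusted for sex (male/female), day-care attendance (yes/no), presence of comorbidities (yes/no), older siblings (yes/no". The synopsis, under Statistical Considerations, repeats the list: "adjusted for sex (male/female), day-care attendance (yes/no), presence of comorbidities (yes/no), older siblings (yes/no". Neither place leaves the list open. Section 11.4.3 does leave further adjustment variables to the SAP, but only for the two-year factorial models.

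**Randomisation.** Section 6.2.1 says that allocation is "stratified by consent to blood tests (yes/no), in randomly permuted blocks of variable length (4 or 8". Sections 7.3 and 9.3.2 add that a child whose baseline blood draw fails is treated as not consenting, and that this is settled before randomisation.

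**Season.** Table 4 (section 9.2) lists, among factors recorded at inclusion, "infant factors (sex, gestational age, season of birth, sepsis" and others. Its footnote says: "Collection of participants' date of birth is needed to determine the season of birth".

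**Day-care.** Table 4 names "childcare attendance (index & siblings" only in the row for potential confounders arising after randomisation. The inclusion rows cover household composition, siblings, smoking and pets, but not childcare. Section 9.3.2 says that the baseline questionnaire asks about exposure, and points to Table 4 for the detail. Section 6.4 treats day-care as an environmental risk factor that randomisation should balance.

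**Comorbidities.** Inclusion criterion 3 (section 7.1.1) requires children "In overall good health, without any clinically significant concomitant disease states". Section 7.1.2 also excludes immunosuppression and severe eczema.

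**The concern.** An analysis should normally condition on the factors that restricted the randomisation and on strong predictors known at baseline, and should not condition on anything that allocation could have changed. The stated list departs from this in two ways.

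First, it leaves out the stratum and season. The outcome window is only three months and section 6.4 plans recruitment over 18 months, so children are observed at different times of year. Leaving a predictor out costs precision.

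Second, the only place where the protocol documents childcare data puts them after randomisation. Parents know the allocation and there is no placebo (section 3.6). If day-care use between 6 and 9 months responds to allocation, adjusting for it no longer gives the total effect of the randomised schedule, which is what the intention-to-treat comparison in section 11.4.1 targets.

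**Working it through.** **Step 1: reproduce the sample size.** Inputs from section 11.2: control rate 0.29 per month, SD 0.32, 30% reduction, two-sided 0.05, 80% power, 85% completion.

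- Difference: 0.30 × 0.29 = 0.087.
- Evaluable per arm: 2 × (1.96 + 0.842)² × 0.32² / 0.087² = 213 after rounding up.
- Randomised per arm: 213 / 0.85 = 251, or 502 in total, against 500 stated.
- With 0.85 × 250 = 212.5 evaluable per arm, power is 80.0%.

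The stated figure reproduces, so the covariate question does not make it wrong.

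**Step 2: how much could season explain under the stated SD?** I read the SD as that of each child's monthly rate over the three months.

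- Mean count: 3 × 0.29 = 0.87. Variance: (3 × 0.32)² = 0.9216.
- Negative binomial dispersion: k = (0.9216 − 0.87) / 0.87² = 0.068.
- Share of variance above Poisson: (0.9216 − 0.87) / 0.9216 = 5.6%.

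The variance of the log rate ratio is proportional to 1/0.87 + 1/0.609 + 2k, where 0.609 = 0.70 × 0.87.

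- With k = 0.068: 1.149 + 1.642 + 0.136 = 2.928.
- With k = 0: 2.791.
- Ratio: 2.791 / 2.928 = 0.953, a reduction of about 5%.

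This is a ceiling. It gives season all the extra-Poisson variance and leaves none for siblings, day-care or sex.

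**Step 3: translate into power, at 212.5 evaluable per arm.**

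| Calculation | Without season | All extra-Poisson variance removed |
|---|---|---|
| Two means, SD 0.32 × √(1 − 0.056) | 80.0% | 82.2% |
| Negative binomial, rate ratio 0.70 | 86.0% | 87.5% |

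The gain is therefore 0 to about 2 points.

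**Step 4: if seasonality comes on top of the stated SD.** The protocol gives no seasonal figure, so the peak-to-trough ratios below are assumptions. Simulation with 425 evaluable children, 1,500 runs per scenario:

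| Assumed peak/trough ratio | Power, unadjusted | Power, season-adjusted |
|---|---|---|
| 1.9 | 85.9% | 86.9% |
| 2.7 | 82.8% | 85.6% |
| 4.1 | 80.2% | 86.5% |

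Simulated type I error was about 5% with and without season.

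**Step 5: day-care.** Two mechanisms, both with assumed inputs.

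- *Infected children leave day-care.* With 40% baseline use, a day-care rate ratio of 1.8 and an exit probability of 0 to 50%, adjusting for the later status moved the estimated rate ratio by less than 0.01, whether the true value was 0.70 or 1.00.
- *Parents change childcare because of allocation.* If use rises from 50% to 60% in the early-MMR arm, with the same rate ratio of 1.8, the total effect is 0.70 × (1 + 0.8 × 0.6) / (1 + 0.8 × 0.5) = 0.70 × 1.48 / 1.40 = 0.74, while the adjusted model reports 0.70.

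Nothing in the protocol suggests a shift of that size. The second case only shows what would have to happen for the bias to matter.

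**The case against.** The strongest reply is that nothing here is a demonstrated error. Children are randomised as they enrol, in blocks of 4 or 8, so the arms stay close to balanced over the calendar and season does not confound the comparison. The blood-consent stratum secures the Part 2 numbers, and no section calls it prognostic. Ignoring it tends, if anything, to make the test conservative. Section 6.4 describes day-care as a baseline characteristic would be described. The draft case report form, listed as an appendix, is not shown and may already ask about it at Visit 1. Details of covariates commonly belong in the SAP.

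Most of this stands. It limits the point to precision and to a timing inconsistency. It does not remove the point, because the protocol fixes a closed list in two places, and the one table that says when childcare is recorded puts it after randomisation.

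A reader might also infer that comorbidities should be dropped as nearly constant. The documents do not establish that. Only clinically significant disease and severe eczema are excluded, so milder conditions remain eligible, and section 6.4 gives a reason for the term. It needs a definition, which the SAP can supply.

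**Conclusion.** The point holds as a modest improvement to the primary model. The list omits the stratification factor and season, both available at randomisation, and leaves the timing of day-care inconsistent between sections 11.4.2, 6.4 and Table 4.

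On the stated mean and SD the gain from season is at most about 5% in the variance of the log rate ratio, or 0 to about 2 points of power. The gain of 1 to 6 points in the simulations needs seasonality beyond that SD, at assumed peak-to-trough ratios of 1.9 to 4.1. No size can be given for the stratum, because the protocol gives no figure on its prognostic value.

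A reader might infer that the primary analysis is invalid, that the trial is underpowered or that the day-care adjustment is biased. The documents support none of these. The sample size reproduces and type I error stays at about 5%. Day-care bias arises only if the status used is post-randomisation, and was below 0.01 on the rate ratio when illness alone drove exit. The gap between 0.74 and 0.70 rests entirely on an assumed behavioural response to allocation.

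**What to change.** 1. In section 11.4.2 and the synopsis, add the blood-consent stratum (yes/no) and calendar season or quarter at randomisation to the primary model.
2. State that day-care attendance means status at Visit 1, before randomisation, and list it among the inclusion data in Table 4. Later childcare can stay in the post-randomisation row for descriptive or exploratory use. Add a baseline questionnaire item only if the case report form lacks one.
3. Keep comorbidities and let the SAP define them.

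The cost is one parameter for the stratum and three for calendar quarters, in about 425 evaluable children, plus wording and possibly one question. The day-care item should be settled early, because status at Visit 1 that was not recorded then can only be recovered by recall.

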## 5. STUDY OUTCOMES

### 5.1 Primary Outcome

#### Stage A

**AIM1:** Number of parent-reported respiratory infections between 6 months and 9 months of age.

*Justification:* As shown in previous studies on the non-specific effect of vaccines, the difference between the two groups is most likely to be seen for respiratory infections, justifying it to be the primary outcome measure. This outcome measure is also clinically relevant given the high burden of disease attributable to respiratory infections in infants.

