### 11.2 Determination of Sample Size

The sample size calculation for the clinical outcome (500 participants) is based on the primary outcome of respiratory infections. Based on the data from a previous trial, we expect a rate of respiratory infection of 0.29 episodes per month (SD 0.32) between 6 and 9 months of age in the control groups (Group C.M. or C.C.). By randomising 500 participants, we will have an 80% power to detect a minimum of 30% reduction in this incidence with a 2-sided p-value of 0.05, assuming at least 85% completion rate of the 9 months questionnaire. The 500 participants will be randomised into 4 groups of similar size (see Section 6 and table 3 in Section 8.1): for the primary outcome analysis, the 250 children receiving early MMR at 6 months of age (Group M.C. or M.M.) will be compared with the 250 children receiving the regular MMR at 9 months of age (Group C.M. or C.C.).

		Timing of the 2 nd MMR		
		2 nd MMR 1m after the 12y DPT-PCV (Modified)	2 nd MMR concomitant to the 12y DPT-PCV (Current)	
Primary outcome comparing the timing of the 1 st MMR	1 st MMR at 6m (Modified)	Group M.M., n=125	Group M.C., n=125	N=250
	1 st MMR at 9m (Current)	Group C.M., n=125	Group C.C., n=125	N=250
		N=250	N=250	

Table 7. Participant allocation in 4 groups; for the primary outcome analysis, the Groups M.C. and M.M. will be compared with the Groups C.M. and C.C. C: current MMR schedule; DTP: diphtheria-tetanus-pertussis vaccine; m: month; M: Modified MMR schedule; PCV: pneumococcal conjugate vaccine.

The sample size calculation for the laboratory outcomes (100 participants) is more conservative as it depends on the success of the blood collection and of the laboratory processing for each of the time points. The use of paired samples (taken from the same infant at different ages) reduces the effect of inter-individual heterogeneity and provides greater statistical power with lower participant numbers.

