### 11.4 Planned Analyses

The full details of the analysis will be provided in the statistical analysis plan, which will be finalised prior to database lock. Briefly, all tests will be 2-tailed and a P<.05 will be considered statistically significant for the primary outcome. Non-parametric tests will be used when variables are not normally distributed.

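### Section 11.4.2 reopens the primary analysis that the synopsis fixes: it also allows a logistic model on any infection, with about 70% power under the protocol's own planning values

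*Protocol*

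**What the plan says.** The synopsis (Statistical Considerations) says that the number of respiratory infections will be compared between the two groups of first-MMR timing "using negative binomial regressions, adjusted for sex (male/female), day-care attendance (yes/no), presence of comorbidities (yes/no), older siblings (yes/no"), with an adjusted incidence rate ratio as the only effect measure.

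The rest of the protocol treats the outcome in the same form. Section 5.1 defines it as "Number of parent-reported respiratory infections between 6 months and 9 months of age". Section 9.2.1 assesses it as an incidence, and the hypotheses in 11.1 concern the number of infections. The sample size in 11.2 rests on a mean rate and its SD: "we expect a rate of respiratory infection of 0.29 episodes per month (SD 0.32) between 6 and 9 months of age".

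Section 11.4.2 opens with the same count. It then allows either a logistic model, if the outcome is dichotomised as 0 versus at least 1, or a negative binomial model, if it is left as a count. The result "will be presented as adjusted odd ratios, hazard ratio, or incidence rate ratios (aIRRs) with 95% confidence interval, according to the model chosen".

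On timing, 11.4 leaves the details to a statistical analysis plan "which will be finalised prior to database lock". Section 11.4.2 places the primary analysis "once all participants have attended the 9 months visit".

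**The concern.** The two statements of the primary analysis cannot both stand. An analysis plan that followed either one could claim to follow the protocol, so the protocol does not define its single confirmatory test.

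The two models also answer different questions. The negative binomial model compares episode rates and uses repeat infections. The logistic model compares the risk of having any infection and ignores every episode after the first. The hazard ratio belongs to neither; Cox regression appears only in 11.4.3 for time-to-event outcomes, and time to first event is a secondary outcome.

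Three things are at stake: which effect the trial estimates, whether the stated power applies to the test used, and whether the 5% level is protected against choosing between two tests.

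**Working it through.** **Inputs (section 11.2).** Control rate 0.29 episodes per month, SD 0.32. The design claims "80% power to detect a minimum of 30% reduction in this incidence with a 2-sided p-value of 0.05". It counts on 85% of the 9-month questionnaires being returned, so with 250 per arm the evaluable number is 250 × 0.85 = 212.5 per arm.

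**1. The plan's own figure.** The difference in mean rate is 0.30 × 0.29 = 0.087. The standard error is 0.32 × √(2/212.5) = 0.0310, so z = 0.087/0.0310 = 2.80. Power = Φ(2.80 − 1.96) = 80.0%. The stated 80% is reproduced as a two-sample comparison of mean rates.

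**2. Turning the planning values into a count.** Over three months the control mean is 3 × 0.29 = 0.87 and the SD is 3 × 0.32 = 0.96. This reads 0.32 as the SD of each child's three-month average rate. A Poisson count would give √0.87/3 = 0.31 on that scale, so 0.32 is plausible. As the SD of a single month's count it would lie below the Poisson value √0.29 = 0.54, so the first reading is the sensible one.

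The protocol states no distribution. I assume a negative binomial matched to these values, with variance μ + kμ²:

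k = (0.96² − 0.87)/0.87² = 0.0516/0.7569 = 0.068

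The mean under a 30% reduction is 0.7 × 0.87 = 0.609, with the same k.

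**3. Count model (Wald test on the log rate ratio).**

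- SE = √[(1/0.87 + 1/0.609 + 2 × 0.068)/212.5] = 0.117
- log rate ratio = ln(1/0.7) = 0.357, so z = 3.04
- Power = Φ(3.04 − 1.96) = 86%

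**4. Logistic option.** P(at least one) = 1 − (1 + kμ)^(−1/k).

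- Control 57.1%, early MMR 44.9%
- log odds ratio = 0.487
- SE = √[1/(212.5 × 0.571 × 0.429) + 1/(212.5 × 0.449 × 0.551)] = 0.196, so z = 2.49
- Power = Φ(2.49 − 1.96) = 70.3%

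A two-proportion test gives 70.6%, and a 20,000-trial simulation with 212 per arm gives 69.5%. For 80% power this option needs 267 evaluable per arm, or 2 × 267/0.85 ≈ 629 randomised, against 500 planned.

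**5. Sensitivity to the assumed distribution (212.5 per arm).**

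| k | Implied monthly SD | Count model | Logistic option |
|---|---|---|---|
| 0 (Poisson) | 0.31 | 88% | 73% |
| 0.068 (matched) | 0.32 | 86% | 70% |
| 0.5 | 0.37 | 76% | 56% |

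The last row does not match the protocol's SD of 0.32, since √(0.87 + 0.5 × 0.87²)/3 = 0.37. It shows only the direction if counts are more dispersed than planned.

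**6. Type I error.** In simulations of 20,000 trials with no effect and 212 per arm, each test alone rejected in about 5%. Rejecting when either test was significant gave about 7.5 to 8%, both at k = 0.068 and at k = 0.5. When the model was instead chosen from pooled data without reference to arm, the rate stayed close to 5%.

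**The case against.** The outcome is stated consistently as a count or rate everywhere else, and dichotomising appears only as a condition in one sentence of 11.4.2. It may be leftover wording that the analysis plan, not shown here, already settles. That makes the repair easy, but the protocol still contradicts itself on its primary test.

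Four stronger readings are tempting, and the documents do not support them.

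- **A reader might infer that the trial's false-positive rate is 8%.** That needs both between-arm tests to be run and the smaller p-value reported. Section 11.4.2 does not describe this; it ties the model to the form of the outcome. Section 6.2.2 keeps those who clean and analyse the data blinded to allocation until the analyses are complete, and a choice made on pooled data leaves the error near 5%.
- **A reader might infer that the analysis plan can follow the primary analysis**, because the last 24-month visit comes up to 15 months after the 9-month visit in an open-label trial. Section 12.2 says the database is locked before release for analysis. With 11.4, the order is plan, lock, analysis. Some doubt remains, since 12.2 speaks of the complete data and no separate 9-month lock is named, but the protocol does not say that the analysis may come first.
- **A reader might infer that the sample size is wrong.** It is not: 11.2 claims 80% only for a reduction in incidence, and that reproduces. No power is claimed for the dichotomy.
- **A reader might infer that section 5.1 also fixes the model.** It names only the count. The model and effect measure are fixed in the synopsis alone.

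**Conclusion.** The contradiction between the synopsis and 11.4.2 is real and concerns the single confirmatory test. Taking the logistic option would replace the episode rate with the risk of any episode. It would also lower power to about 70%, some 10 points below the stated 80% and some 16 below the count model.

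These power figures are conditional on a negative binomial count matched to the stated mean and SD, and on reading 0.32 as the SD of each child's three-month average rate. The direction does not depend on the exact dispersion: even a Poisson count gives the logistic option only about 73%. The error rate of 7.5 to 8% is an upper bound on what the wording leaves open. Blinding and lock before analysis lessen that risk, but they do not settle which estimand is primary.

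**What to change.** In section 11.4.2, delete the logistic option and the odds and hazard ratios. State that the primary analysis is negative binomial regression of the number of respiratory infections between 6 and 9 months, with the covariates already listed, reported as an adjusted incidence rate ratio with 95% confidence interval. List none versus at least one infection as a secondary or sensitivity analysis.

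Optionally, clarify in 11.4 that the statistical analysis plan is final before the data lock for the 9-month primary analysis, and name that lock.

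The cost is a wording amendment. Design, sample size and data collection do not change.
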